8.1.3. Secondary Endpoint

The secondary efficacy endpoints are:

- The proportion of subjects with HBV DNA ≥ 20 IU/mL (as determined by the modified US FDA-defined snapshot algorithm) at Week 96
- The proportion of subjects with HBV DNA < 20 IU/mL and target detected/not detected (i.e. < LLOD) at Weeks 48 and 96, as determined by the modified US FDA-defined snapshot algorithm
- The proportion of subjects with HBeAg loss and proportion with seroconversion to anti-HBe at Weeks 48 and 96

- The proportion of subjects with HBsAg loss and proportion with seroconversion to anti-HBs at Weeks 48 and 96
- The proportion of subjects with normal ALT and proportion with normalized ALT (by central laboratory and AASLD criteria) at Weeks 48 and 96
- The change from baseline in fibrosis as assessed by FibroTest[®] at Weeks 48 and 96

The key secondary safety endpoints are:

- The percent change from baseline in hip bone mineral density (BMD) at Week 48
- The percent change from baseline in spine bone mineral density (BMD) at Week 48
- The change from baseline in eGFR_{CG} (measured by Cockcroft-Gault method) at Week 48

The secondary safety endpoints are:

- The percent change from baseline in hip bone mineral density (BMD) at Week 96
- The percent change from baseline in spine bone mineral density (BMD) at Week 96
- The change from baseline in eGFR_{CG} (measured by Cockcroft-Gault method) at Week 96

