3.1.8. Serologically Evaluable Full Analysis Set

3.1.8.1. Serologically Evaluable Full Analysis Set for HBeAg loss/seroconversion

The Serologically Evaluable Full Analysis Set for HBeAg loss/seroconversion will include all subjects who were randomized and had received at least 1 dose of study drug, and with HBeAg positive and HBeAb negative or missing values at baseline. Subjects will be analyzed according to the treatment they were randomized to during the double-blind phase.

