3.1.9. Open-Label Serologically Evaluable Full Analysis Set

3.1.9.1. Open-Label Serologically Evaluable Full Analysis Set for HBeAg Loss/Seroconversion

The Open-Label Serologically Evaluable Full Analysis Set for HBeAg loss/seroconversion includes all subjects who were randomized and had received at least 1 dose of open-label study

drug, and with HBeAg positive and HBeAb negative or missing at open-label baseline. Subjects will be analyzed according to the treatment they were randomized to during the double-blind phase.

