6.2. Secondary Efficacy Endpoints

6.2.1. Definition of Secondary Efficacy Endpoints

The secondary efficacy endpoints are:

- The proportion of subjects with HBV DNA ≥ 20 IU/mL (as determined by the modified US FDA-defined snapshot algorithm) at Week 96
- The proportion of subjects with HBV DNA < 20 IU/mL and target detected/not detected (ie, < LLOD) at Weeks 48 and 96
- The proportion of subjects with HBeAg loss and proportion with seroconversion to anti-HBe at Weeks 48 and 96
- The proportion of subjects with HBsAg loss and proportion with seroconversion to anti-HBs at Weeks 48 and 96
- The proportion of subjects with normal ALT and proportion with normalized ALT (by central laboratory and AASLD criteria) at Weeks 48 and 96
- The change from baseline in fibrosis as assessed by FibroTest at Weeks 48 and 96

For the final analysis, the following definitions will be used:

- HBsAg loss is defined as HBsAg test result changes from HBsAg positive at baseline to HBsAg negative at a postbaseline visit with baseline HBsAb negative or missing.
- HBeAg loss is defined as HBeAg test result changes from HBeAg positive at baseline to HBeAg negative at a postbaseline visit with baseline HBeAb negative or missing.
- HBsAg seroconversion is defined as HBsAg loss and HBsAb test result changes from HBsAb negative or missing at baseline to HBsAb positive at a postbaseline visit.
- HBeAg seroconversion is defined as HBeAg loss and HBeAb test result changes from HBeAb negative or missing at baseline to HBeAb positive at a postbaseline visit.
- ALT normalization is defined as ALT > ULN (by central laboratory normal range or 2018 AASLD normal range) at baseline but within normal range at a postbaseline visit.

Both baseline and postbaseline borderline serology results will be imputed using the following rules:

- HBsAg and HBeAg borderline will be considered as HBsAg positive and HBeAg positive.
- HBsAb and HBeAb borderline will be considered as HBsAb negative and HBeAb negative.

For the above definitions, baseline will be replaced with open-label baseline for the analyses of subjects in the Open-Label FAS, and with TFFU baseline for the analyses of subjects in the TFFU FAS.

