6.2.2. Analysis Methods for Secondary Efficacy Endpoints

The primary analysis of the proportion of subjects in the Full Analysis Set with HBV DNA ≥ 20 IU/mL (as determined by the modified US FDA-defined snapshot algorithm {U. S. Department of Health and Human Services 2015}) will be repeated for the Week 96 endpoint using the FAS. The Week 96 analysis window is defined as from Study Day 589 to Study Day 840, inclusive.

The analyses for the other secondary efficacy endpoints will be conducted using the FAS. All secondary efficacy endpoints involving proportions will be analyzed from baseline to Week 96 using both the Missing Failure (M F) approach and the Missing Excluded (M E) approach, unless otherwise specified. In the M E approach, all missing data will be excluded in the computation, and in the M F approach, all missing data will be treated as failures and included in both the numerator and denominator. P-values will be calculated using the CMH test stratified by baseline HBeAg status (HBeAg-positive or HBeAg-negative) and age (< 50 or ≥ 50 years), and the proportion difference between the 2 treatment groups and the associated 95% CIs will be calculated based on the stratum-adjusted MH proportion.

The change from baseline in \log_{10} (HBsAg) (IU/mL), both overall and by baseline HBeAg status, and ALT will be summarized by visit using observed data (ie, missing data will be excluded). The p-value, differences in change from baseline in \log_{10} (HBsAg) (IU/mL) and ALT between the 2 treatment groups and the associated 95% CI will be constructed using analysis of variance (ANOVA) models, including treatment group, baseline HBeAg status (HBeAg-positive or HBeAg-negative), and age (< 50 or \geq 50 years) as fixed effects in the model. For the analysis of change from baseline in \log_{10} (HBsAg) (IU/mL) by baseline HBeAg status, only treatment group and age (< 50 or \geq 50 years) will be included as fixed effects in the model.

In addition, the proportion of subjects in the FAS with HBV DNA < 20 IU/mL, the proportion of subjects with normal ALT by the central laboratory and 2018 AASLD criteria (ULN is 35 U/L for males and 25 U/L for females) using the M E approach, and the mean change from baseline in log10 (HBsAg) (IU/mL) and ALT (U/L) will be plotted with 95% CI over time using observed data from baseline to Week 96.

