FibroTest score will be summarized using descriptive statistics (sample size, mean, SD, median, Q1, Q3, minimum, and maximum) by treatment group for subjects in the FAS. The p-value, differences in change from baseline in FibroTest score between the 2 treatment groups and the associated 95% CI will be constructed using ANOVA models, including treatment group, baseline HBeAg status (HBeAg-positive or HBeAg-negative) and age (< 50 or ≥ 50 years) as fixed effects in the model. A shift table of fibrosis stage from baseline based on the FibroTest score at Week 24, 48, and 96 will be provided. Mean change from baseline in FibroTest score will be plotted with 95% CI over time using observed data from baseline to Week 96. A listing of fibrosis assessment by FibroTest will also be provided.

All the analyses of the secondary efficacy endpoints, using both the M F and the M E approach, and plots described above will be repeated for subjects in the Open-Label FAS from open-label baseline to Week 96. No statistical comparisons will be performed.

For subjects in the TFFU FAS, only HBV DNA, ALT, HBsAg, HBeAg loss/seroconversion, and HBsAg loss/seroconversion endpoints will be summarized by visit in the TFFU phase as described above only using the M E approach. No statistical comparisons will be performed.

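### SAP 6.2.2 words Missing = Failure so that missing subjects enter the numerator of success rates, and it gives ALT normalisation no denominator restricted to baseline ALT > ULN

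*SAP*

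**What the plan says.** SAP 6.2.2 analyses the secondary proportions from baseline to Week 96 by both Missing = Failure (M=F) and Missing = Excluded (M=E), with a stratified CMH p-value and a Mantel-Haenszel difference with its 95% CI. It defines M=F by saying that "in the M F approach, all missing data will be treated as failures and included in both the numerator and denominator". (The equals sign in M=F was lost when the text was extracted.)

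On the population, the same paragraph says: "The analyses for the other secondary efficacy endpoints will be conducted using the FAS".

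Two other parts of the SAP bear on that population:

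- SAP 6.2.1: "ALT normalization is defined as ALT > ULN (by central laboratory normal range or 2018 AASLD normal range) at baseline", followed by a value within the normal range after baseline. Subjects with normal ALT at baseline therefore cannot have the event.
- SAP 3.1.8.1 defines a Serologically Evaluable FAS for HBeAg loss and seroconversion, "with HBeAg positive and HBeAb negative or missing values at baseline". SAP 3.1.9.1 defines the open-label version, "with HBeAg positive and HBeAb negative or missing at open-label baseline". Matching sets exist for HBsAg and for treatment-free follow-up (TFFU). SAP 6.2.2 names none of them.

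For TFFU, the listed endpoints are summarised "in the TFFU phase as described above only using the M E approach", so the numerator question does not arise there.

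**The concern.** HBeAg loss, HBsAg loss, the two seroconversions, normal ALT and normalised ALT are all proportions of successes. A subject treated as a failure in such a proportion is counted below the line and not above it. A rule that makes the same subject a failure and also places that subject in the numerator cannot be carried out as written. The SAP is the programming specification, and no other part of it corrects the sentence.

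The denominator matters for a separate reason. If ALT normalisation is divided by the whole FAS, the rate becomes the normalisation rate multiplied by the share of the arm that had raised ALT at baseline. An imbalance in that share then enters the treatment difference. M=E gives no protection, because it removes subjects with missing values and leaves in those who could never normalise.

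**Working it through.** **Inputs.** Protocol 1.2.3, Tables 1-2 and 1-3, give Week 48 counts under M=F from GS-US-320-0108 and GS-US-320-0110. They are used as illustrations. They come from earlier studies, and Table 1-2 is an HBV DNA endpoint. The missing fractions and the share with raised baseline ALT in the present trial are not in the documents.

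**Step 1: reproduce the sponsor's own M=F rates.** With s successes, m subjects without data and N in the FAS, the usual rule is s/N. The literal SAP rule is (s + m)/N.

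| Arm | s | m | N | s/N | (s + m)/N |
|---|---|---|---|---|---|
| 0108 TAF | 268 | 10 | 285 | 94.0% | 97.5% |
| 0108 TDF | 130 | 6 | 140 | 92.9% | 97.1% |
| 0110 TAF | 371 | 27 | 581 | 63.9% | 68.5% |
| 0110 TDF | 195 | 9 | 292 | 66.8% | 69.9% |

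The column s/N matches Table 1-2 in all four arms. The literal rule matches none of them.

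**Step 2: effect of the literal wording.** The rise in each arm is m/N, its missing fraction, whatever the true rate. The crude TAF − TDF difference shifts by the gap between the two missing fractions:

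- 0108: 94.04 − 92.86 = 1.2 points becomes 97.54 − 97.14 = 0.4 points.
- 0110: 63.86 − 66.78 = −2.9 points becomes 68.50 − 69.86 = −1.4 points.

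These are crude differences. Table 1-2 reports stratum-adjusted ones (1.8% and −3.6%).

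**Step 3: denominator for ALT normalisation.** Table 1-3 uses FAS subjects with baseline ALT > ULN. Central laboratory criterion:

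| Study | Denominator | TAF | TDF | Crude difference |
|---|---|---|---|---|
| 0108 | ALT > ULN | 196/236 = 83.1% | 91/121 = 75.2% | 7.8 points |
| 0108 | FAS | 196/285 = 68.8% | 91/140 = 65.0% | 3.8 points |
| 0110 | ALT > ULN | 384/537 = 71.5% | 179/268 = 66.8% | 4.7 points |
| 0110 | FAS | 384/581 = 66.1% | 179/292 = 61.3% | 4.8 points |

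The 0108 difference halves because the shares with raised baseline ALT differ: 236/285 = 82.8% on TAF against 121/140 = 86.4% on TDF. In 0110 the shares are close (537/581 = 92.4% against 268/292 = 91.8%), so only the level moves.

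For the present trial, the FAS rate equals the share with baseline ALT > ULN times the rate among those subjects. At an assumed share of 10%, 20% or 50%, a FAS denominator leaves 10%, 20% or 50% of the normalisation rate.

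**The case against.** The strongest reply is that nobody would program the sentence literally. The method is called Missing = Failure, the same sentence says missing data are failures, Protocol 8.3 and 8.6.2 use the same name, and the tables in Protocol 1.2.3 show the correct practice. The wording may have come from a failure proportion: for HBV DNA ≥ 20 IU/mL, missing counted as failure would indeed sit in the numerator. That does not rescue the sentence, because the Week 96 analysis of that endpoint follows the snapshot algorithm and the protocol exempts it from M=F. The point about intent stands, though. A reader might infer that the sponsor plans to count missing subjects as responders. The documents do not support that, and the 97.5% shows what the words say, not what to expect in the report.

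A reader might also infer that HBeAg loss will be divided by the whole FAS. At the 2:1 HBeAg-negative to HBeAg-positive ratio assumed in Protocol 8.9, a loss rate of 13.8% (Table 1-4, used only as an example) would then fall to 13.8/3 = 4.6%. The documents point the other way. SAP 1.1 states this objective for HBeAg-positive subjects, SAP 3.1.8 to 3.1.10 define sets named for exactly these endpoints, SAP 3.1.5 allows exceptions to the FAS, and SAP 3.2 refers to analyses based on the evaluable sets. What is missing is a cross-reference.

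Finally, a reader might see an undeclared change for HBV DNA < 20 IU/mL. Protocol 8.1.3 has "target detected/not detected (i.e. < LLOD) at Weeks 48 and 96, as determined by the modified US FDA-defined snapshot algorithm", while SAP 6.2.1 has only "target detected/not detected (ie, < LLOD) at Weeks 48 and 96". The protocol synopsis also lists this endpoint without the snapshot phrase, so the protocol itself varies. The difference is not a separate error.

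For ALT normalisation the reply is weaker. The definition and Table 1-3 suggest the right subset, but the SAP neither defines nor names one, and the only population it states is the FAS.

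**Conclusion.** The concern holds as two limited defects in SAP 6.2.2.

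- **The numerator clause is wrong as written** for every success proportion it governs. The intent is plain. Taken literally, the error in each arm equals its missing fraction: 3.1 to 4.6 points across the four illustrative arms (9/292 to 27/581).
- **ALT normalisation has no stated population that fits its definition.** A FAS denominator always lowers the rate unless every subject has raised baseline ALT. It shifts the difference materially only when the arms differ in that share, as in 0108 and not in 0110.

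For HBeAg and HBsAg loss and seroconversion, the only defect in the choice of population is a missing citation.

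The sizes rest on counts from earlier studies. The corresponding figures for this trial are not available, and the Week 48 SAP, which may word these points differently, is not among the documents. The affected endpoints are secondary, lie outside the sequence in Protocol 8.4, and are compared in an exploratory manner under Protocol 8.6.2. The primary endpoint follows the snapshot algorithm and, by SAP 6.1.1, is not re-analysed under this SAP. Its conclusion and the sample size are untouched.

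**What to change.** Amend SAP 6.2.2 as follows.

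(a) Replace the M=F definition with: In the M=F approach, subjects with missing data are counted as non-responders, included in the denominator and not in the numerator.

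(b) State the population for each endpoint:

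- ALT normalisation: FAS or Open-Label FAS subjects with the corresponding baseline ALT > ULN by the criterion in use (central laboratory or 2018 AASLD). If it is also summarised in follow-up, TFFU FAS subjects with TFFU-baseline ALT > ULN.
- HBeAg and HBsAg loss and seroconversion: the matching Serologically Evaluable FAS from SAP 3.1.8, 3.1.9 or 3.1.10.
- Normal ALT: the FAS, as now.

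The cost is three or four sentences. No new data are needed, and the changes follow the conventions of the sponsor's own earlier tables.

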In Study GS-US-320-0108, no subject in either treatment group experienced HBsAg loss by Week 48. In Study GS-US-320-0110, 4 subjects (0.7%) in the TAF group and 1 subject (0.3%) in the TDF group experienced HBsAg loss at Week 48. Three of the 4 subjects in the TAF group and none in the TDF group also experienced HBsAg seroconversion at Week 48.

b AASLD ULN for ALT criteria are as follows: ≤ 30 U/L for males and ≤ 19 U/L for females.

In Study GS-US-320-0110, the proportion of subjects with HBeAg loss or seroconversion to anti-HBe at Week 48 was also evaluated; these data are presented on Table 1-4. A total of 78 (13.8%) and 34 (11.9%) subjects in the TAF and TDF groups, respectively, had HBeAg loss at Week 48. A total of 58 (10.3%) and 23 (8.1%) subjects in the TAF and TDF groups, respectively, experienced HBeAg seroconversion at Week 48.

Table 1-4. GS-US-320-0110: Proportion of Subjects with HBeAg Loss or Seroconversion at Week 48, Missing = Failure (Serologically Evaluable Full Analysis Set)

	GS-US-320-0110			
		TAF 25 mg vs TDF 300 n		s TDF 300 mg
	TAF 25 mg (N = 565)	TDF 300 mg (N = 285)	p-value	Prop Diff (95% CI)
HBeAg Loss, n (%)	78/565 (13.8%)	34/285 (11.9%)	0.47	1.8% (-3.0% to 6.5%)
HBeAg Seroconversion, n (%)	58/565 (10.3%)	23/285 (8.1%)	0.32	2.1% (-2.0% to 6.3%)

P-values were from the Cochran-Mantel-Haenszel test stratified by baseline HBV DNA categories and oral antiviral treatment status. Differences in the proportion between treatment groups and its 95% CI were calculated based on the Mantel-Haenszel proportions adjusted by baseline HBV DNA categories and oral antiviral treatment status strata. Serologically Evaluable Full Analysis Set for HBeAg loss/seroconversion included subjects who were HBeAg positive and HBeAb negative/missing at baseline. HBeAg loss was defined as changes from HBeAg-positive at baseline to HBeAg-negative at a post-baseline visit with baseline anti-HBe negative/missing. HBeAg seroconversion was defined as HBeAg loss and anti-HBe change from negative/missing at baseline to positive at a post-baseline visit. Source: GS-US-320-0110 Week 48 CSR, Section 15.1, Table 19.1

Virologic Resistance Analysis

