8.6. Efficacy Analysis

8.6.1. Primary Analysis

The primary analysis will be performed when the last subject has completed Week 48 assessments or discontinued prematurely. The primary analysis will consist of a non-inferiority evaluation of efficacy of TAF versus TDF, with respect to the proportion of subjects with HBV DNA \geq 20 IU/mL at Week 48 (as defined by the modified FDA snapshot Algorithm). It will be concluded that TAF is not inferior to the TDF if the upper bound of the two-sided 95% confidence interval of the difference between treatment arms (TAF arm – TDF arm) in the response rate is less than 4% (i.e., a margin of 4% is applied to non-inferiority assessment). The 95% confidence interval will be constructed using the normal approximation method based on stratified Mantel-Haenszel proportions, where stratification factors are HBeAg status (HBeAg positive or negative) and age (\geq 50 or < 50 years).

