1.3. Sample Size and Power

With respect to the primary efficacy endpoint of proportion of subjects with HBV DNA \geq 20 IU/mL (the lower LOQ of the current polymerase chain reaction [PCR] assay), as determined by the modified US FDA-defined snapshot algorithm, at Week 48, when the sample sizes are 230 (TAF 25 mg arm) and 230 (TDF 300 mg arm), a two-group, large-sample normal approximation test of proportions with a one-sided 0.025 significance level will have 80% power to establish non-inferiority of TAF to TDF. It is assumed that both treatment arms will have subjects who have HBV DNA \geq 20 IU/mL (as defined by the modified US FDA-defined snapshot algorithm) at a rate of 2.4% at Week 48 (based on the rates of suppressed subjects having HBV DNA \geq 29 IU/mL, the lower LOQ of the assay used in those studies, after 48 weeks of treatment from the combined data from TDF studies GS-US-174-0102 and GS-US-174-0103 with the ratio of HBeAg- to HBeAg+ subjects assumed to be 2:1), with a non-inferiority margin of 4%.

The proposed sample size (n 230 for the TAF 25 mg arm, n 230 for the TDF 300 mg arm) also provides > 99% power to detect a 1.81% difference in the percentage change from baseline in hip BMD at Week 48 (assuming a 1.47% [SD 2.71%] change from baseline in the TAF 25 mg arm and 0.34% [SD 2.83%] change from baseline in the TDF 300 mg arm, with a two-sided α 0.05); a > 99% power to detect a 2.00% difference in the percentage change from baseline in spine BMD at Week 48 (assuming a 1.56% [SD 3.84%] change from baseline in the TAF 25 mg arm and 0.44% [SD 4.14%] change in the TDF 300 mg arm, with a two-sided α 0.05); a 97% power to detect a 4.9 mL/min difference in the change from baseline in eGFR_{CG} at Week 48 (assuming a 1.3 mL/min [SD 13.2] change from baseline in the TAF 25 mg arm and 3.6 mL/min [SD 13.0] change from baseline in the TDF 300 mg arm, with a two-sided α 0.05). These assumptions were derived from an HIV switch study (GS-US-292-0109) due to the unavailability of stable and suppressed switch data from TAF HBV studies.

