7.4.3. Estimated Glomerular Filtration Rate

Estimated glomerular filtration rate will be summarized for subjects in the Safety Analysis Set from baseline to Week 96.

The following formulae will be used to calculate eGFR:

• CG based:

```
eGFRcg (mL/min) [(140 age (yrs)) \times weight (kg) \times (0.85 if female)] / (SCr (mg/dL) \times 72), where weight is actual total body mass in kilograms, and SCr is serum creatinine.
```

• CKD-EPI Creatinine based:

```
eGFRCKD EPI, creatinine (mL/min/1.73 m^2) 141 \times \min(SCr/\kappa, 1)^{\alpha} \times \max(SCr/\kappa, 1)^{1.209} \times 0.993^{age} \times 1.018 (if female) \times 1.159 (if black),
```

where κ is 0.7 for females and 0.9 for males, α is 0.329 for females and 0.411 for males, min indicates the minimum of SCr/ κ or 1, and max indicates the maximum of SCr/ κ or 1 {Levey 2009}.

• CKD-EPI Cystatin C based:

```
eGFRCKD EPI, cysC (mL/min/1.73 m^2) 133 \times min(SCys/0.8, 1)^{0.499} \times max(SCys/0.8, 1)^{1.328} \times 0.996^{age} [\times 0.932 \text{ if female}],
```

where SCys is serum cystatin C.

P-values for the baseline, the change from baseline in eGFR $_{CG}$ and eGFR $_{CKD}$ $_{EPI,\ creatinine}$ will be estimated from the 2-sided Wilcoxon rank sum test to compare the 2 treatment groups. For eGFR $_{CKD}$ $_{EPI,\ cysC}$, only the baseline value will be summarized as the postbaseline tests were only performed as reflex tests.

The number and proportion of subjects with decrease from baseline of $\geq 25\%$ and $\geq 50\%$ in eGFRcg and eGFR ckd EPI, creatinine will be summarized by treatment groups for subjects in the Safety Analysis Set from baseline to Week 96. Statistical comparisons of the subject incidence rates between the 2 treatment groups during the entire study period will be performed using Fisher's exact test.

The number and proportion of subjects in each stage of chronic kidney disease (CKD) will be summarized by baseline stages of CKD at Weeks 12, 24, 36, 48, 60, 72, and 96 for the entire study treatment period based on subjects in the Safety Analysis Set. The distribution of the stages of CKD at these visits will be compared between the 2 treatment groups adjusting for entire study treatment period using rank ANCOVA {LaVange 2008}.

The stages of CKD are defined as follows:

- Stage 1: eGFRcg≥ 90 mL/min
- Stage 2: eGFRcg \geq 60 and \leq 90 mL/min
- Stage 3: eGFRcg \geq 30 and \leq 60 mL/min
- Stage 4: eGFRcg < 30 mL/min

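### SAP 6.2.2 gives HBsAg loss and seroconversion a CMH p-value and a Mantel-Haenszel interval but no rule for zero or very few events, which the sponsor's own rates make likely

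*SAP*

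**What the plan says.** SAP 6.2.1 lists among the secondary efficacy endpoints "The proportion of subjects with HBsAg loss and proportion with seroconversion to anti-HBs at Weeks 48 and 96". SAP 6.2.2 sets one method for the whole class: "All secondary efficacy endpoints involving proportions will be analyzed from baseline to Week 96 using both the Missing Failure (M F) approach", and also with missing data excluded. It adds that "P-values will be calculated using the CMH test stratified by baseline HBeAg status" and age group, and that "the proportion difference between the 2 treatment groups and the associated 95% CIs will be calculated based on the stratum-adjusted MH proportion".

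SAP 6.2.2 gives no variance formula and no rule for zero or few events. For the primary endpoint, Protocol 8.6.1 describes the interval as a "normal approximation method based on stratified Mantel-Haenszel proportions". SAP 3.3 allows strata with too few subjects to be combined, which is the only sparse-data provision.

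Elsewhere the SAP does use an exact method. For large eGFR declines, section 7.4.3 says "Statistical comparisons of the subject incidence rates between the 2 treatment groups during the entire study period will be performed using" Fisher's exact test.

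Protocol 1.2.3 gives the only HBsAg rates: "In Study GS-US-320-0108, no subject in either treatment group experienced HBsAg loss by Week 48". In the HBeAg-positive study, 4 TAF subjects and 1 TDF subject lost HBsAg by Week 48; 3 and 0 of these seroconverted.

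**The concern.** The CMH test and the MH interval are large-sample methods, and these two endpoints were known in advance to be very rare. If neither arm has an event, the CMH statistic is 0/0. An MH interval with the usual variance then has zero width, which reports exact equality from about 230 subjects per arm. Combining strata does not help, because the shortage is of events and not of subjects.

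Comparing serological response between arms is a stated secondary objective (SAP 1.1). Without a rule, the presentation would have to be settled after the programmer meets a missing p-value or a zero-width interval.

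**Working it through.** **Inputs.** 230 subjects per arm and an HBeAg-negative to HBeAg-positive ratio of 2:1 (SAP 1.3), so 460/3 = 153.3 HBeAg-positive subjects, 76.7 per arm. Earlier study sizes are 285 + 140 = 425 (HBeAg-negative) and 581 + 292 = 873 (HBeAg-positive), 1298 in all (Protocol Table 1-1).

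**The plan's own figures.** The non-inferiority formula gives n = (1.960 + 0.842)² × 2 × 0.024 × 0.976 / 0.04² = 229.8, so the 230 per arm reproduces. The HBsAg percentages also reproduce: 4/581 = 0.7% and 1/292 = 0.3%.

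**Expected events at Week 48, and P(no event) = exp(−E).** The documents state no expected number, so three bases are shown. The Week 96 columns assume that events double.

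| Endpoint and basis | E, Week 48 | P(none) | E doubled | P(none) |
|---|---|---|---|---|
| Loss, arm-specific: 76.7 × (4/581 + 1/292) | 0.79 | 45% | 1.58 | 21% |
| Loss, arms pooled: 153.3 × 5/873 | 0.88 | 42% | 1.76 | 17% |
| Loss, both studies pooled: 460 × 5/1298 | 1.77 | 17% | 3.54 | 3% |
| Seroconversion, arm-specific: 76.7 × 3/581 | 0.40 | 67% | 0.79 | 45% |
| Seroconversion, arms pooled: 153.3 × 3/873 | 0.53 | 59% | 1.05 | 35% |
| Seroconversion, both studies pooled: 460 × 3/1298 | 1.06 | 35% | 2.13 | 12% |

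The first two bases for each endpoint use a rate of 0 in HBeAg-negative subjects (0/425). Applying the HBeAg-positive rate to all 460 subjects, as an upper bound, gives 460 × 5/873 = 2.63 losses at Week 48.

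**What the methods return.** Four strata per arm of about 77, 76, 39 and 38 are assumed (ages split evenly). With w = n1·n0/(n1 + n0) in each stratum:
- difference d = Σw(p1 − p0)/Σw
- plain variance = Σw²[p1(1 − p1)/n1 + p0(1 − p0)/n0]/(Σw)²
- CMH denominator = Σ n1·n0·m(T − m)/[T²(T − 1)], where m is the events and T the subjects in the stratum

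With m = 0 everywhere, the variance and the CMH numerator and denominator are all 0. The Sato variance is also 0.

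| Events | Plain MH 95% CI | CMH p | Score (Miettinen-Nurminen) 95% CI, unstratified | Fisher p |
|---|---|---|---|---|
| 0 vs 0 | 0.0% to 0.0% | undefined | −1.6% to 1.6% | 1 |
| 1 vs 0 | −0.4% to 1.3% | 0.32 | −1.2% to 2.4% | 1 |
| 2 vs 0 | −0.3% to 2.1% | 0.16 | −0.8% to 3.1% | 0.50 |

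The Newcombe half-width at 0/230 versus 0/230 is 3.84/(230 + 3.84) = 1.64%. An MH variance with 0.5 added to the counts gives about ±1.7% at zero events.

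**Coverage of the plain MH interval (simulation, 400,000 trials).** The arms are given the same HBeAg-positive rate, 5/873. Coverage is 99.9% at that rate, 99.0% at twice it and about 97.5% at three times it.

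**The case against.** Four objections carry weight.

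**Coverage.** A reader might infer that coverage falls far below 95%. Taking 4/581 and 1/292 as the true rates does give simulated coverage of 55%, and 79% and 87% at two and three times those rates. But this treats a difference built on five events as real, about 0.12 percentage points over the whole trial, and counts a zero-width interval as missing it. With equal arms, coverage is about 98% or more. Nor is the interval shown to undercover once events occur. In the unequal-rates simulation, trials with at least one event have coverage of 99.9%, 99.0% and 95.3% at one, two and three times the rates. The documents therefore do not support a claim of poor coverage.

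**Zero width is not certain.** The SAP does not state its variance, and the Week 48 SAP to which it refers is not available. The sponsor's earlier intervals hint at a correction. Protocol Table 1-2 reports −3.6% to 7.2% for the HBeAg-negative study, a half-width of 5.4. Simulated stratum layouts matching those totals gave 4.8 to 5.3 with a plain variance and 5.4 to 5.9 with a 0.5 correction. The HBeAg seroconversion interval in Table 1-4 (−2.0% to 6.3%, half-width 4.15) points the same way. This is suggestive only, because stratum sizes are not given. It does not rescue the CMH p-value, which is undefined at zero events whichever variance is used.

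**Time point and population.** This SAP governs the final analysis, and the Week 48 analysis had already been done (SAP 2.2). By Week 96 both arms have received TAF and more events may have accrued. The earlier subjects were viremic at entry, so their rates are only a proxy for suppressed subjects. Both points are fair, and they are why the Week 96 chance of no loss is put at 3% to 21%.

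**Consequence.** Protocol 8.6.2 makes these tests optional and exploratory, and they lie outside the procedure in Protocol 8.4. The counts would be visible beside any odd interval. This limits the importance of the point but does not remove it.

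**Conclusion.** The point holds as a gap in specification. SAP 6.2.2 prescribes a large-sample p-value and interval for two endpoints expected to produce about 0.8 to 1.8 losses and 0.4 to 1.1 seroconversions among 460 subjects at Week 48. If no event occurs, the p-value does not exist, and the interval collapses unless an unstated correction is in use. With one or two events, results are defined but differ visibly from score and exact results: at 2 versus 0, p is 0.16 by CMH and 0.50 by Fisher.

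The sizes rest on the earlier studies' rates, the 2:1 HBeAg mix and, for Week 96, the assumption that events double. The point does not extend to the primary non-inferiority interval. It is a worthwhile, low-cost improvement and no threat to the trial's main conclusions.

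**What to change.** In SAP 6.2.2, prespecify by endpoint that HBsAg loss and HBsAg seroconversion are compared using:
- a stratified Miettinen-Nurminen score interval, or an exact interval, for the difference; and
- Fisher's exact test, as SAP 7.4.3 already does for eGFR declines, or an exact stratified test.

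Name the endpoints instead of switching on an observed count, so that the method does not depend on the data. Keep CMH and MH for the commoner endpoints, and state which MH variance is used there.

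The cost is one or two sentences and a check that the software version in SAP section 10 offers the chosen method. Intervals will be slightly conservative, and Fisher's test drops the stratification, which matters little with so few events.
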